
 To assess the safety and tolerability of IV administration of LASN01 compared with placebo in patients with TED 	
For randomized treatment arms:
 
 Treatment-emergent adverse events, changes in concomitant medications compared with placebo Changes from Baseline in clinical laboratory evaluations, vital signs, electrocardiograms, ophthalmic assessments, and physical examinations following study drug administration compared with placebo 

Secondary: Pharmacokinetics	

 To characterize the pharmacokinetic profile of IV administration of LASN01 in patients with TED 	
For all treatment arms:
 
 Serum LASN01 concentrations at specified timepoints
Exploratory: Immunogenicity	

 Characterize the immunogenicity of IV administration of LASN01 in patients with TED 	
For all treatment arms:
 
 Incidences of antidrug antibodies at specified timepoints relative to Baseline
Exploratory: Clinical	

 To assess orbital, muscle, and fat compartment volumes and confirm change in proptosis To assess TED-related signs and confirm change in CAS, lid retraction and eye movement To assess responder rate in TED-related clinical parameters 	
For randomized treatment arms:
 
 MRI imaging of the orbit assessing change from Baseline in proptosis as well as in orbital, muscle, and fat parameters at Week 9, 13, 29, 41, 53, and 73; LASN01 treatment arm compared to placebo Facial imaging of the eye assessing mean values, change from earliest timepoint collected, and change from baseline (when available) in conjunctival redness, MRD1 and MRD2, and eye movement at Week 9, 13, 17, 21, 25, 29, 37, 45, 53, and 73

Objectives	Corresponding Endpoints
	
 • Responder analyses assessing TED-related clinical parameters in either eye 

Exploratory: Pharmacodynamics	

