9.2.5. Safety Analyses

Safety will be assessed in the Safety Analysis Population.

Safety will be evaluated by presenting listings and summaries of AEs, vital signs, 12-lead ECGs, ophthalmic assessments, conventional clinical laboratory evaluations (serum chemistry, hematology, coagulation, and UA evaluations), prior and concomitant medication use, treatment compliance, and exposure. Safety variables will be tabulated by treatment arm, LASN01 dose level and placebo. Other safety measures (eg, physical examination findings, pregnancy test results, drug screening test results) will be listed.

AEs will be coded using the MedDRA version 24.1 or higher. The incidences of TEAEs will be presented by system organ class and preferred term according to MedDRA, by relationship to the study drug, by severity, and by whether or not they resulted in alteration of administration of or discontinuation of study drug. A TEAE is defined as an AE that occurs during or after the first study drug infusion. A TRAE is defined as an AE with a plausible temporal relationship between the onset of the AE and administration of study drug (and as further defined in [Table 6](#)). TEAEs will be captured until Day 365/Week 53. From this visit to the EOS visit, only TRAEs will be recorded. In addition, the incidences of serious TEAEs and TEAEs leading to discontinuation of study drug will be presented by system organ class, preferred term, and relationship to study drug.

Descriptive statistics and change from Baseline for clinical laboratory test and vital sign results will be presented by scheduled time point. Incidences of potentially clinically significant clinical laboratory results, determined based on normal ranges, will also be summarized by scheduled time point. The numbers and percentages of abnormal 12-lead ECGs will be provided by scheduled time point.

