To assess the safety and tolerability of IV administration of LASN01 compared with placebo in patients with TED	
For randomized treatment arms:
 
 Treatment-emergent adverse events (TEAEs), changes in concomitant medications compared with placebo Changes from Baseline in clinical laboratory evaluations, vital signs, electrocardiograms, ophthalmic assessments, and physical

CONFIDENTIAL

The contents of this document are confidential to [REDACTED]
 Unauthorized use, disclosure, or reproduction is strictly prohibited.

	
examinations following study drug administration compared with placebo
 
For open-label treatment arm(s):
 
 • TEAEs, changes in concomitant medications • Changes from Baseline in clinical laboratory evaluations, vital signs, electrocardiograms, ophthalmic assessments, and physical examinations following study drug administration
Secondary: Pharmacokinetics	
To characterize the pharmacokinetic (PK) profile of IV administration of LASN01 in patients with TED	
For all treatment arms:
 
 • Serum LASN01 concentrations at specified time points
Exploratory: Immunogenicity	
Characterize the immunogenicity of IV administration of LASN01 in patients with TED	
For all treatment arms:
 
 • Incidences of antidrug antibodies at specified timepoints relative to Baseline
Exploratory: Pharmacodynamics	
To explore the potential pharmacodynamic profile of IV administration of LASN01 in patients with TED	
For all treatment arms:
 
 • Protein markers in blood relevant to the Interleukin-11 (IL-11) pathway

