6.2.1 PARTIAL OR MISSING DATES

Partial or missing dates required to identify treatment-emergent or concomitant data will be imputed.

For partial or missing start and end dates of AEs and concomitant medications, the following rules apply:

Partial or Missing Start Dates:

- Missing Day Only: Impute as the 1st of the month, unless the month and year match the first dose date, then impute the day of the first dose.
- Missing Day and Month: Impute as January 1st, unless the year matches the first dose year, then impute the day and month of the first dose.
- Completely Missing Date: Impute as the first dose date unless the end date is on or before the first dose date; in that case, impute as January 1st of the end date's year.

Partial or Missing End Dates:

- Missing Day Only Impute as the last day of the month, unless the month and year match the last dose date, then impute the day of the last dose.
- Missing Day and Month: Impute as December 31st, unless the year matches the last dose year, then impute the day and month of the last dose.
- Ongoing Flag Missing or "Yes": Do not impute the end date unless a death date is available; then impute as the death date.
- Ongoing Flag "No": Impute the missing end date as the last dose date.
- Lost to Follow-Up or Withdrawal Without End Date: Use the last known participation date as the end date.
- Imputed Date After Death Date: Set the end date equal to the death date.

Original dates will be displayed in data listings, and imputed dates will be used only for derivations (e.g., study day, treatment-emergent status).

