9.1 Prior and Concomitant Medications

Prior and concomitant medications will be coded using World Health Organization Drug Dictionary (WHODrug), with the version specified in the DMP.

Prior medications are those with an end date before the initiation of the study drug. Concomitant medications are those taken (1) before initiation of study drug administration and continuing after the first administration, or (2) at any time following the first administration of the study drug.

Both prior and concomitant medications will be listed. Ocular and non-ocular outputs will be generated separately.

A separate listing will be presented for current TED treatments.

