11.3 Analysis of the Exploratory Efficacy Variables

11.3.1 ORBITAL IMAGING AND FACIAL PHOTOGRAPHY FROM CENTRAL READING CENTER

Axial high-resolution images will be obtained locally and transmitted to a central radiology vendor for review. Besides assessment of proptosis, the orbital magnetic resonance imaging (MRI) sequences may provide (but are not limited to) volumetric analysis (in mm³) of orbital compartments such as individual extraocular

CONFIDENTIAL

The contents of this document are confidential to [REDACTED]
Unauthorized use, disclosure, or reproduction is strictly prohibited.

muscle volume and total muscle volume, orbital fat volume, fibrosis measurement of each muscle and average fibrosis of all 4 four muscles per eye. These will be measured at screening and for all visits according to the schedule of assessments and will all be presented as listings. The proptosis listing will include both proptosis readings and the average reading for each visit for the study and fellow eye.

A facial photography assessment will also be done per the ophthalmology manual. Facial photography measurements may be performed and, if present, these will be presented as a listing.

In the US only, an orbital computed tomography (CT) scan may be performed if the patient cannot have an MRI scan.

12. Safety Analyses

All safety analyses will be conducted using the Safety Population. Safety endpoints will be summarized for the LASN01 300 mg, LASN01 600 mg, [REDACTED], placebo, and for the All Patients treatment arms.

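### The SAP specifies only a patient listing for a primary safety endpoint defined as a comparison with placebo, and does not declare the reduction

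*SAP*

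**What the plan says.** - **Endpoint.** Under Primary: Safety for the randomized arms, Protocol Section 3 has "Treatment-emergent adverse events, changes in concomitant medications compared with placebo". SAP Section 2 repeats it: "Treatment-emergent adverse events (TEAEs), changes in concomitant medications compared with placebo".
- **Protocol analysis.** Protocol 9.2.5 plans both listings and summaries of a set of items that includes "prior and concomitant medication use, treatment compliance, and exposure". It adds: "Safety variables will be tabulated by treatment arm, LASN01 dose level and placebo".
- **SAP analysis.** SAP 9.1 codes medications in WHODrug and defines prior and concomitant. It then says "Both prior and concomitant medications will be listed", with ocular and non-ocular outputs separate and a further listing of current TED treatments. It gives no count, percentage or between-arm display.
- **SAP safety section.** Section 12 opens with "Safety endpoints will be summarized for the LASN01 300 mg, LASN01 600 mg" and goes on to name placebo and all patients. Subsections 12.1 to 12.12 contain nothing on medications, and the list of safety assessments in SAP 2.1 omits them.
- **Precedence and changes.** SAP Section 1 gives the SAP's methods precedence over the protocol's. Section 16 moves the remaining secondary and exploratory endpoints to listings and says nothing about a primary safety endpoint.
- **Dates.** For a medication flagged as not ongoing, SAP 6.2.1 says "Impute the missing end date as the last dose date".

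**The concern.** The endpoint has two parts: a change, and a comparison with placebo. A listing by patient supplies neither as a result; it supplies the raw records from which someone could later derive one. SAP 9.1 counts as concomitant both a drug continued from before the first dose and a drug begun afterwards, so the SAP's own classification does not isolate change. Nor does either document say what counts as one: a new drug, a dose change or a stop.

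At stake is prespecification of a named primary safety endpoint. If the table is built after unmasking, the definition of change, the drug grouping and the counting rule will all be chosen with the data in view. There is also a practical interest. Protocol 6.8.2 allows otherwise prohibited drugs when needed to treat an adverse event, so a display of co-medication by arm and drug class would help in reading both safety and efficacy.

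**Working it through.** The plan attaches no figure to this endpoint, so the check is a comparison of texts, followed by a trace of the date rule.

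1. **Is it a primary safety endpoint in both documents?** Yes. Protocol Section 3 and SAP Section 2 agree, and both specify comparison with placebo for the randomized arms.

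2. **Did the protocol plan more than a listing?** Yes. Protocol 9.2.5 names medication use among the items to be listed and summarized, and tabulates safety variables by arm, dose level and placebo.

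3. **Does the SAP keep that?** Not in any specific section available. Section 9.1 stops at listings, and Section 12 has no medication subsection. Its opening sentence promises summaries of safety endpoints by arm, which conflicts with 9.1 but names no variable or statistic for medications.

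4. **Is the reduction declared?** No. Section 16 limits efficacy tables to Hertel proptosis and Total CAS and reduces other secondary and exploratory endpoints. SAP Section 1 also says that only the proptosis responder and Total CAS endpoints will be summarized. Read literally, that would remove every safety summary. Section 12 then specifies summaries of adverse events, vital signs, ECGs and laboratory data, so the sentence can only concern efficacy.

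5. **How much is affected?** The randomized-arm primary safety objective has two bullets, and this is one of the two components of the first. SAP Table 1 plans 8 patients per arm, so one patient is 1/8 = 12.5% of an arm.

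6. **Would the 6.2.1 date rule disturb a by-arm count?** Take a drug stopped before the first dose, end date missing, ongoing flag No.
   - The end date becomes the last study-dose date. Under 9.1 a prior medication must end before study drug starts, so the record is no longer prior.
   - If the start date is known and precedes the first dose, the drug is derived as continuing into treatment. It could also be counted as a stop on study.
   - If the start date is wholly missing, it becomes the first-dose date. The exception for an end on or before the first dose no longer applies once the end has been imputed to the last dose. The record then runs from first to last dose and could be counted as a new start if the first-dose day is included.
   - SAP 6.2.1 displays original dates in listings and uses imputed dates only for derivations. The error therefore reaches derived status and any count built on it, not the listing.

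**The case against.** A reader might infer several stronger things, and the documents do not support them.

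- **That the trial cannot report the endpoint.** It can. The data are collected and WHODrug-coded, SAP 6.3 presents listings with treatment arm, and SAP Section 1 allows additional required analyses in the study report. With about 24 randomized patients, counts could be made from the listing. What is missing is a prespecified summary.
- **That no table is planned anywhere.** This cannot be verified. Section 18.1 appears in the SAP's contents, but its text was not available. If a table is there, 9.1 still has to be aligned with it.
- **That no other output bears on co-treatment.** SAP Section 7 summarizes by arm the discontinuations of treatment for prohibited medication, and any, major and minor deviations, with deviation details listed. Section 9.1 lists current TED treatments. None of these counts medication by drug class and arm, and permitted drugs need not appear in the Section 7 summaries.
- **That a listing cannot distinguish a new drug from a continued one.** Where a start date is recorded, it can.
- **That a Week 37 difference is uninterpretable without the table.** The arms are randomized, and a descriptive count of medications taken after randomization would not separate co-treatment from treatment effect either.
- **That an old steroid course would be displayed as on-study use.** The listing would show its missing dates; only derived status would be wrong. The entry criteria also require the interval since the last oral steroid for TED to be established before Screening, which makes such records less likely for those drugs.

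It is also fair to say that this is an early-terminated proof-of-concept study and that the endpoint is descriptive. That limits the weight of the point. It does not remove the mismatch between a stated primary safety endpoint and an output that does not deliver it.

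**Conclusion.** The point holds in a limited form. In the text available, the only specific output for this primary safety endpoint is a listing. That falls short of the endpoint's own wording and of Protocol 9.2.5, conflicts with the opening of SAP Section 12, and is not declared in Section 16. This is more than missing detail, because the SAP states an output that does not answer its own endpoint.

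The scale is modest: part of one bullet, in a study with 8 patients planned per arm, where each patient moves an arm's percentage by 12.5 points. Actual arm sizes may differ. The conclusion assumes that Section 18.1 contains no medication table. The date-rule problem is secondary; it matters only for derived prior or concomitant status, and so for the table proposed below.

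**What to change.** - **SAP 9.1.** Add one Safety Population table using the SAP's safety columns, which include 300 mg, 600 mg and placebo. Give the number and percentage of patients with at least one medication newly started after the first dose, by WHODrug class. Add changed or stopped medications only where the eCRF captures them; neither document says that it records dose changes. Define change in the text, including how the first-dose day is treated.
- **SAP 6.2.1.** For that table, do not let the last-dose end-date rule class as concomitant a medication that is recorded as stopped before the first dose.
- **SAP Sections 12 and 16.** Refer to the table from Section 12 and record the definition in Section 16. If the sponsor prefers to keep a listing only, Section 16 should instead state the removal and the reason, and Section 12's opening should be qualified.
- **SAP 18.1.** Check the table list against whichever choice is made.

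The cost is one table from coded data plus SAP wording. The table is descriptive and should be labelled so; it will not separate co-treatment from treatment effect at Week 37.

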9.2 Prior and Concomitant Procedures

Prior and concomitant procedures will be coded using MedDRA with the version specified in the DMP. Prior and concomitant have the same definitions as the medications stated in [Section 9.1](#) but for procedures. A listing of prior and concomitant procedures will be provided.

10. Dosing Compliance and Treatment Exposure

In addition to the analyses described in the following sections, patient listings will be provided for study drug administration.

CONFIDENTIAL

The contents of this document are confidential to [REDACTED]
Unauthorized use, disclosure, or reproduction is strictly prohibited.

10.1 Dosing Compliance

The number of actual doses received will be calculated from the number of infusions recorded in the study drug administration electronic Case Report Form (eCRF). The number of expected doses will depend on which protocol amendment the patient is consented to, regardless of study completion status.

Number of doses received will appear on the Disposition listing; otherwise, study drug administration will have its own listing.

10.2 Treatment Exposure

Extent of treatment exposure for completed or discontinued patients will be calculated in days using the following:

$$\text{Extent of Exposure (days)} = (\text{Date of Last Dose} - \text{Date of First Dose}) + 1$$

Extent of treatment exposure for each patient exposed to study drug will be summarized with continuous descriptive statistics for each treatment arm, pooled active group (300 mg and 600 mg), and for all patients using the Safety Population.

11. Efficacy Analyses

11.1 Analysis of Primary Efficacy Endpoint(s)

The primary efficacy endpoint is the percent of patients showing a response in proptosis measured using Hertel exophthalmometer (≥ 2 mm decrease from baseline) in the study eye and separately in either eye without increased proptosis (≥ 2 mm increase) in the other eye at Week 37 (Day 253) as measured by Hertel Exophthalmometer. The primary efficacy endpoint will be assessed with a one-sided Fisher's exact p-value comparing the pooled active group to placebo at each visit, including the primary endpoint visit at Week 37. Interpretation of statistical significance should be made at the $\alpha=0.1$ level. Two-sided 95% CIs for responder analyses may be calculated with the Clopper-Pearson exact method.

Fisher's exact test syntax:

```
Proc sort data = <data>;
    by TRTPN descending AVALC; *orders the responses;
run;

proc freq data=<data> order=data; *Keeps the order in the dataset;
    tables TRTPN*AVALC / fisher;
run;

where TRTPN is planned treatment (1=Active and 2=Placebo)
```

CONFIDENTIAL

The contents of this document are confidential to [REDACTED]
Unauthorized use, disclosure, or reproduction is strictly prohibited.

AVALC is the responder variable (Y = response in proptosis of ≥ 2 mm decrease from baseline in the study eye and separately in either eye and < 2 mm increase in the other eye; and N = response of < 2 mm decrease from baseline in the study eye and separately in either eye or ≥ 2 mm increase in the other eye).

Note: with the above ordering, the right-sided p-value will be the correct one-sided p-value from Fisher's exact test for the primary hypothesis.

The primary efficacy analysis will utilize the Efficacy Population with LOCF. Additional sensitivity analysis may be conducted on the primary efficacy endpoint with observed data only (ODO) using study eye.

The percentage of proptosis responders by treatment arm (pooled active group and placebo) over time through Week 37 using line graphs for the Efficacy Population with LOCF will be produced for study eye and either eye separately.

Tables and figures will be provided for the individual treatment groups and pooled active group for all available visits while Week 37 remains the primary endpoint.

. A listing of proptosis in both eyes will be provided.

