2.2 Statistical Hypotheses

The primary clinical endpoint will be assessed using a one-sided Fisher's exact test at a 0.10 significance level. This analysis combines the 600 mg and 300 mg Q4W treatment arms ("pooled group") and compares them to placebo.

- Null Hypothesis (H_0): At Week 37, the percentage of patients showing a proptosis response in the study eye without deterioration in the fellow eye and separately in either eye is less than or equal in the LASN01 pooled group (300 mg and 600 mg) compared to placebo.
- Alternative Hypothesis (H_1): At Week 37, this percentage is greater in the LASN01 pooled group compared to placebo.

3. Study Design and Procedures

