11.2.1 CLINICAL ACTIVITY SCORE

The CAS measures the presence (scored as 1) or absence (scored as 0) of the following signs and symptoms:

- Spontaneous orbital pain
- Gaze-evoked orbital pain
- Eyelid swelling due to active TED
- Eyelid erythema
- Conjunctival redness due to active TED
- Chemosis
- Inflammation of the caruncle or plica

CONFIDENTIAL

The contents of this document are confidential to [REDACTED]
Unauthorized use, disclosure, or reproduction is strictly prohibited.

Total CAS is the sum of these scores and is measured at the appropriate visits according to the schedule of assessments. A CAS responder is defined as patients achieving a Total CAS score of 0 or 1 at a post-baseline visit. A CAS Responder must have at least a score of 2 at baseline to be included in analyses. Study eye and either eye responder analyses will use a one-sided Fisher's exact p-value to compare the individual treatment arms and pooled active group to placebo at each visit.

Two-sided 95% CIs for responder analyses may be calculated with the Clopper-Pearson exact method.

Total CAS and its change from baseline results will be summarized for each visit with descriptive statistics for each individual arm and the pooled active group. P-values for the one-sample t-tests will be provided to assess each individual arm and the pooled treatment arm change from baseline. The 95% CIs may also be constructed around the treatment difference, and p-values from a two-sample t-test will be provided to assess the individual treatment arm and the pooled active treatment differences as compared to placebo. An analysis of covariance (ANCOVA) model with baseline and treatment group as fixed factors will be used to compare pooled active group to placebo for study eyes and separately for either eyes at each visit.

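### The SAP's Fisher code prints the wrong tail when no active patient responds and at least one placebo patient does

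*SAP*

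**What the plan says.** SAP Section 2.2 sets a one-sided alternative: "At Week 37, this percentage is greater in the LASN01 pooled group compared to placebo". SAP Section 11.1 says the endpoint is "assessed with a one-sided Fisher's exact p-value comparing the pooled active group to placebo at each visit, including the primary endpoint visit at Week 37", judged at an alpha of 0.10, and prints SAS code. The code sorts "by TRTPN descending AVALC; *orders the responses", runs PROC FREQ with ORDER=DATA, and requests "tables TRTPN*AVALC / fisher". Treatment is coded 1 for active and 2 for placebo; response is the character value Y or N. A Note then says that "with the above ordering, the right-sided p-value will be the correct one-sided p-value" for the primary hypothesis.

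Section 11.1 also promises proptosis tables for the individual dose groups at all available visits. Section 11.2.1 uses a one-sided Fisher p for CAS responders "to compare the individual treatment arms and pooled active group to placebo at each visit", but gives no code for it. Neither document fixes the column order in another way or mentions a table with no active responders.

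**The concern.** Under ORDER=DATA, column levels follow their first appearance in the sorted data. Active records come first. If any active patient responds, the first record is active/Y, column 1 is Y, and the right-sided p is the intended tail. If none responds, the first record is active/N and column 1 is N. Cell (1,1) then counts active non-responders, so the right-sided p asks whether LASN01 has more failures than placebo.

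The error runs in one direction: a correct p of 1 is replaced by a smaller value, at exactly those visits where only placebo patients responded. A reader who scans p-values by visit in a signal-seeking study could take a result that favours placebo as support for LASN01.

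**Working it through.** **Inputs.** Planned sizes are 8 per arm, so 16 pooled active v 8 placebo (SAP Section 4 and Table 1). Alpha is 0.10, one-sided (SAP Sections 2.2 and 11.1). Planned response rates are 65% for LASN01 and 15% for placebo, with 10% as the alternative placebo rate (SAP Section 4).

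**The plan's own figure first.** Exact enumeration of Binomial(16, 0.65) against Binomial(8, 0.15), rejecting when the one-sided hypergeometric tail is at most 0.10, gives 81.8% power. With a 10% placebo rate it gives 89.7%. The SAP states approximately 81% and 90%, so the intended test and tail are as described.

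**Where the code departs from the intended tail.** Emulating the sort and the data-order rule over every possible table for 16 v 8 and 8 v 8, the printed right-sided p equals the intended one whenever at least one active patient responds. It differs only at zero active responders. If neither group responds there is one column and no p-value, so the fault also needs at least one placebo responder.

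**Size of the wrong p.** With n1 active and n2 placebo patients, zero active responders and b placebo responders, the code prints the probability that all b responders fall on placebo:

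p = C(n2, b) / C(n1 + n2, b)

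The intended tail, P(active responders ≥ 0), is 1.

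| Placebo responders | 0/16 active: printed p | 0/8 active: printed p | Correct p |
|---|---|---|---|
| 1/8 | 8/24 = 0.333 | 8/16 = 0.500 | 1.000 |
| 2/8 | 28/276 = 0.1014 | 28/120 = 0.233 | 1.000 |
| 3/8 | 56/2024 = 0.0277 | 56/560 = 0.1000 | 1.000 |
| 4/8 | 70/10626 = 0.0066 | 70/1820 = 0.0385 | 1.000 |
| 5/8 | 56/42504 = 0.0013 | 56/4368 = 0.0128 | 1.000 |

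A printed p at or below 0.10 therefore needs at least 3 of 8 placebo responders, and 0/8 v 3/8 only ties at 0.1000.

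**How often, if both groups respond at 10%** (an illustrative common rate):

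- Any flip is (1 − 0.10)^n1 × [1 − (1 − 0.10)^8]. For 16 v 8: 0.1853 × 0.5695 = 10.6%. For 8 v 8: 0.4305 × 0.5695 = 24.5%.
- A flip that prints p ≤ 0.10 replaces the second factor by P(at least 3 of 8) = 0.0381. For 16 v 8: 0.1853 × 0.0381 = 0.7%. For 8 v 8: 0.4305 × 0.0381 = 1.6%.
- About 93% of flips therefore print a p above 0.10 (1 − 0.0381/0.5695).

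**Effect on the false-positive rate, if both groups respond at 15%.** The chance of p ≤ 0.10 rises from 0.7% to 1.5% for 16 v 8 and from 3.0% to 5.8% for 8 v 8. Both stay below the nominal 10%.

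**Week 37.** At a 65% active rate, zero of 16 has probability 0.35^16 = 5 × 10⁻⁸, and power stays at 81.8%. If the active rate were only 15% or 10%, zero of 16 would have probability 7.4% or 18.5%.

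**The case against.** The strongest reply is that the Note speaks only of the primary hypothesis, which is the pooled comparison at Week 37. Under the planning assumptions the faulty table will not occur there. This stands as a limit on scope. It does not rescue the Note, because the same table can occur at Week 37 if the drug has little effect, and Section 11.1 itself applies the test at every visit.

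A second reply is that the template names no visit variable. If all visits were run as one stratified table, data-order levels should be set over the whole input, and a single active responder at any visit would put Y first throughout. This also stands: the fault is certain only when the code is run on one visit at a time, which the SAP neither requires nor rules out.

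Third, no CAS code is printed, so its reach to CAS responders and single-dose arms depends on the template being reused. It is plausible there: a CAS responder must reach 0 or 1 (SAP Section 11.2.1) while entry requires a CAS of at least 4 (Protocol Section 5.1), so an 8-patient arm could easily have no responder early on. The documents give no CAS responder rate.

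Fourth, response percentages are tabulated beside the p-values, so 0% against 37.5% with p = 0.028 would look wrong to an attentive reader. Non-primary visits carry no decision rule, and SAP Section 6.4 disclaims multiplicity control. These points lower the severity but do not make the printed p correct.

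**Conclusion.** The point holds as a coding fault of minor to moderate importance. The stated rule gives the reversed tail whenever the analysed dataset has no active responder and at least one placebo responder, and neither document corrects it.

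A reader might infer three stronger things that the documents do not support:

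- That the planned primary result is compromised. At a 65% rate it is practically untouched.
- That every flip yields a favourable-looking p. One or two placebo responders print values above 0.10.
- That 11% and 25% are the chances of false significance. They are the chances of any wrong p; a wrong p at or below 0.10 has a chance of about 0.7% or 1.6% per table at a 10% rate.

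The conclusion rests on standard PROC FREQ behaviour, emulated rather than run in SAS: levels ordered by first appearance, and the right-sided p referring to cell (1,1). The code comments show that the SAP relies on the data order too. The figures use the planned 16 and 8; SAP Section 1 reports early termination, so actual sizes may differ.

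**What to change.** Make the column order independent of the data. For example, code response numerically (1 = Y, 2 = N) and use ORDER=INTERNAL, so that column 1 is Y whenever any patient responds. Reword the Note to say that the right-sided p refers to the active/Y cell.

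Add a programmed check that p = 1 when active has no responders and placebo has at least one. Report p as not estimable when neither group has a responder. A check that simply demanded p = 1 for zero active responders would fail in that last case, which at a 10% rate is 0.9^24, about 8% of 16 v 8 tables. State in Section 11.1 whether visits are run separately, and whether the same code serves the single-dose arms and CAS responders.

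Re-check any output already produced with this code. SAP Section 15 reports a completed interim analysis with unmasked outputs, though not whether this code was used for it.

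The cost is one line of code, a few sentences in the SAP and one validation check. No result that is now correct would change.
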